6.3.3. List of permitted concomitant medications

- Hydroxycarbamide used to control leucocytosis is allowed
- Haematopoietic growth factors used in the centre may be prescribed after Cycle 1 for the subsequent cycles
- Anti-emetics are strongly recommended for prophylaxis prior each S64315 administration and dexamethasone mandatory at least before S64315 LID1, LID2 and CID2 (see [section 8.2.8.1](#))
- Anti-diarrhoeals should be prescribed if clinically indicated except for prophylaxis prior to first dose of S64315. If prophylaxis or treatment is required subsequently to the first S64315 administration, it may be administered at the discretion of the investigator (see [section 8.2.8.2](#))

The patient must be informed to notify the investigational site about any new medications he/she takes after having signed the ICF of the study. All medications (other than IMPs) and significant non-drug therapies (including physical therapy, herbal/natural medications and blood transfusions) administered during the study must be listed in the eCRF.

Treatments received for the studied disease and after the last IMPs administration are to be recorded in 'Post-withdrawal follow-up' eCRF form.

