8.2.8. Gastrointestinal disorders

8.2.8.1. Nausea and vomiting management

Considering the GLP toxicity studies and the preliminary clinical data with S64315 (as of September 5, 2019, 23 (60.5%) and 19 (50%) out of 38 patients treated in the S64315 single agent AML and MDS study experienced nausea and vomiting respectively), nausea/vomiting prophylaxis is strongly recommended before each S64315 infusion.

Dexamethasone administration is mandatory at least 1h before S64315 infusion on the days of L1D1 and L1D2, and on C1D2.

Based on international guideline ([ASCO, 2011](#)), this prophylaxis consists in a two-drug combination of palonosetron and dexamethasone, before each S64315 infusion, followed by dexamethasone maintenance for two days after each S64315 infusion.

According to azacitidine E.U. SmPC, patients should be premedicated with anti-emetics for nausea and vomiting.

The recommended prophylaxis is displayed in the [Table \(8.2.8.1\) 1](#).

Table (8.2.8.1) 1 - Treatments schedule for nausea/vomiting prophylaxis

LID1 and LID2	Palonosetron 0.25 mg IV or 0.5 mg p.o.+ Dexamethasone 8 mg p.o. / IV 1h before each S64315 infusion, followed by dexamethasone 8 mg p.o. / IV during two days after each S64315 infusion, as required
CxD ₁	Metoclopramide IV before azacitidine administration
CxD ₂	Palonosetron 0.25 mg IV or 0.5 mg per os (p.o.) before azacitidine administration + Dexamethasone 8 mg p.o. / IV. 1h before S64315 infusion
CxD ₃	Dexamethasone 8 mg p.o. / IV. as required
CxD ₄	Dexamethasone 8 mg p.o. / IV. as required
CxD ₉	Palonosetron 0.25 mg IV or 0.5 mg p.o.+ Dexamethasone 8 mg p.o. / IV before each
CxD ₁₆	S64315 infusion, followed by dexamethasone 8 mg p.o. / IV during two days after each
CxD ₂₃	S64315 infusion, as required

If palonosetron is not available, clinicians may substitute with a first-generation 5-HT₃ serotonin receptor antagonist (i.e. granisetron/ dolasetron/ tropisetron, to be used with caution according to ‘Guidance on use of co-medication for CL1-64315-004 clinical study’).

Limited evidence also supports adding aprepitant to the combination, if the above combination does not provide sufficient nausea/vomiting control.

As a reminder, ondansetron is prohibited along the study due to the risk of QTcF prolongation (see ‘Guidance on use of co-medication for CL1-64315-004 clinical study’).

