10.4.4.2. Safety

The safety analyses will be performed on the SS sets, SS1 and SS2, by dose level and overall.

DLT until the end of Cycle 1

Number and percentage of patients in the DLTES with DLT occurrence from the LID period to the end of the first cycle will be tabulated by dose level and overall.

DLT after the end of Cycle 1

Number and percentage of patients evaluable for DLTs, with occurrence of DLT after the end of the first cycle will be tabulated by dose combination and overall.

Emergent adverse event

NCI CTCAE v5.0 will be used to classify all adverse events.

Number of Emergent adverse event (EAE), number and percentage of patients reporting at least one EAE will be summarised by System Organ Class and Preferred Term, overall and by dose level. The same analysis will be performed for serious EAEs and SAEs.

Some analyses will be performed by worst on-treatment grade, severity, relationship to the IMP, outcome and action taken.

Clinical laboratory evaluation

Laboratory parameters will be graded according to NCI CTCAE v5.0. For laboratory tests where grades are not defined by NCI CTCAE v5.0, results will be classified according to the laboratory reference ranges.

The following summaries will be generated separately for each haematology and biochemistry tests:

- for laboratory tests where grades are defined by NCI CTCAE v5.0, shift tables comparing the worst on-treatment grade to the grade at baseline
- for laboratory tests where grades are not defined by NCI CTCAE v5.0, shift tables comparing the classification according to the laboratory normal ranges to baseline

Urinalysis abnormalities will be described using shift tables comparing the worst on-treatment value (Positive, Trace, Negative) to the value at baseline.

Physical examination including vital signs, body weight and ECOG PS

These criteria will be described using baseline value, worst on-treatment value and change from baseline to worst on-treatment value.

ECG parameters and LVEF

Quantitative parameters (QT interval corrected and LVEF) and qualitative parameters (ECG abnormalities) will be described.

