3.4.4. Clinical laboratory evaluation

Descriptive statistics on quantitative value and value by grade at baseline and worst grade on treatment according to the grade at baseline will be provided for gradable parameters (see [Table \(3.4.4\) 1](#)).

Table (3.4.4) 1 – Gradable parameters

Parameter		Worst Highest	Worst lowest	Gradable at baseline*
Blood biochemistry	Alanine aminotransferase (ALT)	High ALT	NA	No
	Albumin	NA	Low albumin	Yes
	Alkaline phosphatase (ALP)	High ALP	NA	No
	Amylase	High amylase	NA	Yes
	Aspartate aminotransferase (AST)	High AST	NA	No
	Bilirubin (total)	High total bilirubin	NA	No
	Cholesterol (total)	High cholesterol	NA	Yes
	Creatine phosphokinase (CPK)	High CPK	NA	Yes
	Gamma-glutamyl transferase (gamma-glutamyl transpeptidase) (GGT)	High GGT	NA	No
	Creatinine (serum)	High serum creatinine	NA	Yes
	Glucose	NA	Hypoglycemia	Yes
	Lypase	High lipase	NA	Yes
	Magnesium	Hypermagnesemia	Hypomagnesemia	Yes
	Potassium	Hyperkalemia	Hypokalemia	Yes
	Sodium	Hypernatremia	Hyponatremia	Yes
	Triglycerides	High triglycerides	NA	Yes
	Ionized calcium	High ionized calcium	Low ionized calcium	Yes
Blood haematology	Haemoglobin	High haemoglobin	Anemia	Yes for Low / No for High
	Lymphocytes	NA	Low lymphocytes	Yes
	Neutrophils	NA	Low neutrophils	Yes
	White blood cells (WBC)	NA	Low WBC	Yes

	Platelets	NA	Low platelets	Yes
Blood coagulation	Activated partial thromboplastin time (aPTT)	High aPTT	NA	Yes

Descriptive statistics on quantitative value and value by reference ranges at baseline and worst value on treatment according to baseline, with respect to the lower-limit normal (LLN) and the upper-limit normal (ULN) or by classes (<LLN / [LLN-ULN] / >ULN or normal / mild / moderate / severe for creatinine clearance) will be provided for non-gradable parameters (see [Table \(3.4.4\) 2](#)) and for parameters gradable post-baseline but non-gradable at baseline, in which case only baseline values will be presented.

Table (3.4.4) 2 – Non Gradable parameters

Parameter		Worst Highest	Worst lowest
Blood biochemistry	Bicarbonates	NA	Low bicarbonates
	Uric acid	High uric acid	NA
	Calcium (total)	Hypercalcemia	Hypocalcemia
	Creatinine clearance (approximated by the Modification of Diet in Renal Disease Glomerular Filtration Rate (MDRD GFR))	NA	Low creatinine clearance (Normal/mild/moderate/severe)
	Direct bilirubin	High direct bilirubin	NA
	High-density lipoprotein (HDL)	High HDL	NA
	Lactate dehydrogenase (LDH)	High LDH	NA
	Low-density lipoprotein (LDL)	High LDL	NA

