	Phosphorus	NA	Hypophosphatemia
	Troponin I	High troponin I	NA
	Troponin T	High troponin T	NA
	Urea	High urea	NA
	Urea nitrogen (blood) (BUN)	High BUN	NA
Blood haematology	Basophils	NA	Low basophils
	Eosinophils	High eosinophils	NA
	Haematocrit	High haematocrit	Low haematocrit
	Monocytes	High monocytes	NA
	Red Blood Cell (RBC) Count	High RBC	Low RBC
	Lymphocytes	High lymphocytes	NA

	White Blood Cell (WBC) Count	High WBC	NA
Thyroid function	T3 free	High T3 free	Low T3 free
	T4 free	High T4 free	Low T4 free
	Thyroid Stimulating Hormone (TSH)	High TSH	Low TSH
Cardiac markers	Creatine PhosphoKinase Myocardial Band (CPK-MB) activity	High CPK-MB activity	NA
	CPK-MB mass	High CPK-MB mass	NA
	Brain Natriuretic Peptide (BNP)	High BNP	NA
Blood coagulation	International normalized ratio (INR)	High INR	NA

For urinalysis parameters haematuria, glycosuria, proteinuria, ketonuria: Descriptive statistics at baseline and worst value on treatment period, by classes (negative, trace, positive).

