4.2.3.4. Clinical laboratory evaluation**Values**

Only reliable values are considered for analyses. Unreliable values are flagged into the database.

WBC differentiation, including values of neutrophils, basophils, eosinophils, monocytes, lymphocytes and blasts, will be ignored if blast value is missing/not done or the differentiation is automated, as considered not reliable.

In case of **multiple samples**:

- Each post-baseline value (test, re-test, planned, unplanned) measured under treatment is taken into account for analyses.

Units

All parameters will be analysed in international units (IU).

Abnormal values

Abnormal values are described according to:

- Reference laboratory ranges for the non-gradable parameters.
- NCI-CTCAE version 5.0 grade for gradable parameters.

Laboratory reference limits and NCI-CTCAE version 5.0 grades are reported in the database.

For the parameters which are gradable according to CTCAE v5.0, the grades will be derived using the local laboratory reference limits in analysis datasets.

Table (4.2) 4 - Definition of CTCAE grade - Version 5.0 - Gradable parameters

Parameter	Grade 1	Grade 2	Grade 3	Grade 4
Sodium (mmol/l) – Hypernatremia]ULN;150]]150;155]]155;160]	>160
Sodium (mmol/l) - Hyponatremia	[130;LLN[-	[120;130[< 120
Potassium (mmol/l) – Hyperkalemia]ULN;5.5]]5.5;6]]6;7]	> 7
Potassium (mmol/l) – Hypokalemia		[3.0;LLN[[2.5;3.0[< 2.5
Amylase (IU/L) - High	>ULN – 1.5 x ULN	>1.5 x ULN – 2 x ULN	>2 x ULN – 5 x ULN	> 5 x ULN
Triacylglycerol Lipase (IU/L) - High	>ULN – 1.5 x ULN	>1.5 x ULN – 2 x ULN	>2 x ULN – 5 x ULN	> 5 x ULN
Ionized calcium (mmol/l) - High]ULN;1.5]]1.5;1.6]]1.6;1.8]	> 1.8
Ionized calcium (mmol/l) - Low	[1.0;LLN[[0.9;1.0[[0.8;0.9[< 0.8
Magnesium (mmol/l) - Hypermagnesemia]ULN;1.23]	-]1.23;3.30]	> 3.30
Magnesium (mmol/l) - Hypomagnesemia	[0.5;LLN[[0.4;0.5[[0.3;0.4[< 0.3
Albumin (g/l) - Low	[30; LLN[[20; 30[< 20	-
Glucose (mmol/l) - Hypoglycemia	[3.0;LLN[[2.2;3.0[[1.7;2.2[< 1.7
Total cholesterol (mmol/l) - High]ULN;7.75]]7.75;10.34]]10.34;12.92]	> 12.92
Triglycerides (mmol/l) - High	[1.71;3.42]]3.42;5.7]]5.7;11.4]	> 11.4
Serum creatinine increased (umol/L)	>ULN – 1.5 x ULN	>1.5 x baseline – 3.0 x baseline (if baseline available) OR >1.5 x ULN – 3.0 x ULN	>3.0 x baseline (if baseline available) OR >3.0 x ULN – 6.0 x ULN	>6.0 x ULN

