- Normal renal function (MDRD_GFR >90 mL/min/1.73m²).
- Mild renal impairment (MDRD_GFR 60-90 mL/min/1.73m²).
- Moderate renal impairment (MDRD_GFR 30-59 mL/min/1.73m²).
- Severe (MDRD_GFR <30mL/mn/1.73m²).

Worst value

Worst value will be analysed as follow:

- For the urinalysis parameters, the worst class will correspond to 'Positive' class, then 'Trace' and finally 'Negative' will be considered as normal class.
- For creatinine clearance, the worst class will correspond to "severe" category, then "moderate", then "mild" and finally "normal".
- Baseline and post baseline worst grade for High and Low:
 - Low: If the result is below lower normal range limit, low =grade (for gradable parameter) or result (for non-gradable parameter), Else low=0.
 - High: If the result is above upper normal range limit, high =grade (for gradable parameter) or result (for non-gradable parameter), Else high =0.

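### The SAP plans no on-treatment laboratory summary of high blood glucose, although dexamethasone is mandatory before three early infusions

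*SAP*

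**What the plan says.** SAP 1.2 keeps laboratory tests, including blood biochemistry, among the endpoints of the primary safety objective. SAP 3.4.4 splits the tests into two tables. Gradable parameters are in Table (3.4.4) 1, summarised by CTCAE grade. Non-gradable ones are in Table (3.4.4) 2, summarised against the laboratory limits.

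- **Table (3.4.4) 1.** The glucose row reads "Glucose NA Hypoglycemia Yes": nothing for the highest value, hypoglycaemia for the lowest, gradable at baseline.
- **Table (3.4.4) 2.** There is no glucose row. The table does carry the high direction for two parameters that Table (3.4.4) 1 handles only when low, WBC and lymphocytes ("High lymphocytes").
- **Table (4.2) 4.** The only glucose entry is "Glucose (mmol/l) - Hypoglycemia".
- **Worst-value rule, SAP 4.2.3.4.** "Low: If the result is below lower normal range limit, low =grade (for gradable parameter) or result (for non-gradable parameter), Else low=0".

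On premedication, Protocol 8.2.8.1 states "Dexamethasone administration is mandatory at least 1h before S64315 infusion" on the two lead-in days and C1D2, and Protocol 6.3.3 says the same. Table (8.2.8.1) 1 gives 8 mg as part of the recommended prophylaxis at every infusion, with further doses on the two following days as required.

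**The concern.** Glucose is in the biochemistry panel of Protocol Table (8.2) 1, so the values will be in the database. The SAP summarises them in one direction only. A corticosteroid given before the first S64315 infusion, and before at least two more, makes the other direction the one a safety reader would look for.

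As written, the laboratory section would report hypoglycaemia and say nothing about values above ULN. The single glucose table may also be misread. SAP 4.2.3.4 describes grade 0 as a value within the limit or reference range, yet a patient whose glucose is well above ULN is placed there too.

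**Working it through.** There is no figure to reproduce, so the check is a search of every place where blood glucose could be summarised on treatment.

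| Place in SAP | Low glucose | High glucose |
|---|---|---|
| Table (3.4.4) 1 | yes, by grade | NA |
| Table (3.4.4) 2 | no row | no row |
| Table (4.2) 4 | grades 1 to 4 | no entry |
| Worst-value rule, 4.2.3.4 | grade if below LLN | scored low = 0 |
| Urinalysis, 3.4.4 | not applicable | urine glucose only: negative, trace, positive |
| Baseline description, 3.4.4 | quantitative value | quantitative value, before treatment only |

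No row gives on-treatment blood glucose above ULN.

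**How the SAP treats other one-directional parameters.** Table (3.4.4) 1 has 23 parameters. Five are summarised in both directions: magnesium, potassium, sodium, ionized calcium and haemoglobin. That leaves 23 − 5 = 18 in one direction, of which glucose is one. Of the other 17, two (WBC and lymphocytes) receive the opposite direction in Table (3.4.4) 2 and 17 − 2 = 15 do not. Albumin, neutrophils and platelets are low-only with no high row, exactly like glucose. The mechanism exists in the SAP, but it is not the SAP's general rule.

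**Whether relevant samples are collected.** Protocol 8.2.2 schedules fasted biochemistry 24h and 48h after the end of LID1 and of LID2, and biochemistry at the end of the C1D2 infusion. That is 2 + 2 + 1 = 5 scheduled post-infusion samples per patient who reaches C1D2. Dexamethasone is given at least 1h before an infusion lasting at least 2h. Measured from the mandatory dose, the samples therefore fall at:

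- C1D2 end of infusion: at least 1 + 2 = 3h.
- 24h lead-in samples: at least 1 + 2 + 24 = 27h.
- 48h lead-in samples: at least 1 + 2 + 48 = 51h.

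The lead-in samples also follow any as-required doses given on the days after infusion. Most other biochemistry samples are predose and may be taken up to 3 days earlier (24h for C1D2), so before that day's premedication. The additional 8h, 24h and 72h draws after C1D2 and the 24h draw after C1D9 are limited to AST, ALT and total bilirubin.

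**Whether glycosuria fills the gap.** Urinalysis is scheduled at inclusion, LID1 predose, D1 of each cycle predose, and withdrawal. From D23 to the next D1 is 28 − 23 + 1 = 6 days, or 3 days at the early end of the 3-day predose window. None of the scheduled urine samples is timed to the day or two after an infusion.

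**The case against.** The strongest reply is that this row follows the SAP's majority pattern. A reader might infer from WBC and lymphocytes that the SAP always adds the ungraded direction to Table (3.4.4) 2 and forgot glucose. The count above does not support that, since 15 of the 17 comparable parameters are left in one direction.

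A reader might also infer a breach of Protocol 10.4.4.2, which plans "for laboratory tests where grades are not defined by NCI CTCAE v5.0, shift tables comparing the classification according to the laboratory normal ranges to baseline". That sentence divides the laboratory by test, not by direction. The SAP defines grades for glucose, so glucose can be read as falling under the companion provision for graded tests, which the SAP meets with the hypoglycaemia grades. Extending the sentence to each ungraded direction of a graded test would equally require high platelets and high neutrophils.

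Nor is it right that high glucose can never appear in the report. Protocol 8.2 requires a laboratory abnormality with clinical impact to be reported as an adverse event, and SAP 3.4.2 tabulates those by SOC and PT. Glycosuria is summarised by class.

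Finally, the documents do not list hyperglycaemia among the identified risks (Protocol Table (8) 1) or the expected overlapping toxicities (Protocol 2.3.4). The link from dexamethasone to high glucose is general clinical knowledge. Dexamethasone is mandatory at three infusions only.

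All of this stands and limits the point. It does not supply the missing summary. Adverse-event reporting depends on clinical impact or investigator judgement, urine glucose is a different measurement at different times, and baseline glucose says nothing about change on treatment.

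**Conclusion.** The point holds as a free improvement, not as an error in the plan. No planned on-treatment laboratory summary covers blood glucose above ULN, and the one glucose table scores such values as no abnormality.

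What is lost is descriptive: mainly shifts above ULN that no investigator reported as an adverse event. The DLT assessment, the MTD and the BLRM are unaffected. How many patients would show a high value cannot be derived from the documents.

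Two assumptions matter. One is that dexamethasone can raise glucose, which the documents do not state. The other is that the separate table shells, which were not available, follow the SAP tables and do not already add a high-glucose output.

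**What to change.** Add a row to Table (3.4.4) 2 under blood biochemistry: Glucose, worst highest = High glucose, worst lowest = NA. Present the worst highest on-treatment value against baseline in the classes <LLN / [LLN-ULN] / >ULN, in the same format as high WBC and high lymphocytes. Keep the hypoglycaemia grades in Table (3.4.4) 1 and Table (4.2) 4 unchanged.

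A footnote to the glucose grade table, saying that grade 0 there means not below LLN and may include values above ULN, would prevent misreading.

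The cost is one SAP row, one footnote and one output. The glucose values and laboratory reference limits are already collected.

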Creatine kinase (CK) / Creatine phosphokinase (CPK)	Grade ≥ 3 serum CK/CPK Grade 3 isolated electrolyte abnormalities (i.e. those occurring without clinical consequence) not recovered with or without intervention, to Grade < 2 level within 72 hours

TOXICITY	DLT CRITERIA
Electrolyte abnormalities (including magnesium, calcium, phosphorus, etc.) clinically significant	Any Grade 4 electrolyte abnormality
Cardiac disorders	QTcF interval \geq 501 ms or increase of $>$ 60 ms from baseline on at least two separate ECG assessments (1 assessment = triplicate ECG) Asymptomatic, absolute decrease in LVEF of 10% or greater from baseline AND LVEF $<$ 50% Asymptomatic, absolute decrease in LVEF of 20% or greater from baseline Troponin increase $>$ 10xULN or a troponin increase consistent with the diagnosis of a myocardial infarction (Grade 3) Symptomatic congestive heart failure
Skin and subcutaneous tissue disorders	Grade \geq 3 rash
Haematological abnormalities	Grade 4 neutropenia and/or thrombocytopenia persisting for 28 days after the start of azacitidine dosing in a cycle of therapy in the absence of active AML ($<$ 5% blasts) or active MDS or myelofibrosis
Other AEs	Any Grade \geq 3 AE Single event or multiple occurrences of the same event that lead to a dosing delay of $>$ 7 days in a cycle may be considered to be DLT by the Investigators and the Sponsor, even if not Grade \geq 3 Failure to restart test drug administration at the same dose due to drug-related toxicity Failure to restart test drug administration at the same dose within one cycle (i.e. 28 days) of the first missed dose due to delayed recovery from drug-related toxicity Failure to initiate cycle 1 after completing the LID period or failure to receive LID2 after receiving the LID1, due to drug-related toxicity
NCI CTCAE v5.0 will be used for grading	

The following criteria will not be considered as DLT:

- Grade 3 nausea, vomiting, diarrhoea, anorexia or constipation that do not result in hospitalization, tube-feeding or use of TPN
- Grade 3 fatigue, asthenia, fever
- Grade 3 isolated electrolyte abnormalities (i.e. those occurring without clinical consequence) that resolve, with or without intervention, to Grade $<$ 2 level in 72 hours

Patients who meet any of the criteria included in Table (4.1.3.5) 2 at the end of Cycle 1 will not be evaluable for DLT and therefore will be replaced during the dose escalation phase I part of the study, but not in the expansion parts of the study.

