8.2.5.3. Cardiac marker follow-up

In order to monitor a potential cardiac toxicity, a cardiac marker assessment, including troponin, CPK-MB and BNP, will be performed at predose, 6h, 24h, 48 and 72h after S64315 EoI on the days of LID1 (D-13) and LID2 (D-6), C1D2 and C1D9 and at each pre-dose assessments for the following visits.

Either troponin I or T assessment can be used, but it should be ultra-sensitive, whenever possible. The same subtype (either I or T) should be used throughout the study. If, for a given centre, both troponin I and T can be assessed, priority should be given to troponin I.

In case of troponin increase observed after any of the first two S64315 infusions during cycle 1 (C1D2 or C1D9), it will be recommended to assess these cardiac markers at 48h and 72h S64315 EoI and after each subsequent S64315 infusions (before discharge and beyond, if needed) on a regular basis according to the investigator's judgment.

In case of troponin increase $> 10\times\text{UNL}$ or a troponin increase consistent with the diagnosis of a myocardial infarction (Grade 3), the patient should discontinue study treatment (see [section 8.12](#)).

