NOTE: Upon discontinuation due to LVEF decrease, closely monitor LVEF until resolution. The same cardiac imaging modality (i.e. transthoracic echocardiography (TTE) or MUGA scan) used at baseline is to be used for all subsequent assessments	
Cardiac MRI abnormality	In case of cardiac MRI abnormality clinically significant according to the cardiologist (e.g. compatible with ischemia or left ventricular dysfunction), in a context of troponin elevation, discontinue patient from study drug treatments
Cardiac biomarkers	
Grade 1 troponin I or T elevation	Omit dose, evaluate and treat patient per institutional guidelines. Follow Troponin I/T to resolution per institutional guidelines 
 - If no evidence of LVEF decrease from baseline of 10% or greater on TTE or MUGA* and Troponin I/T resolves to normal in \leq 7 days, then maintain dose level - If no evidence of LVEF decrease from baseline of 10% or greater on TTE or MUGA* and Troponin I/T resolves to normal in $>$ 7 days, then \downarrow 1 dose level. Consult with a cardiologist prior to re-initiating test drug - If evidence of LVEF decrease from baseline of 10% or greater on TTE or MUGA, follow guidelines for LVEF decrease

	*exams to be performed once per cycle or according to physician decision A clear investigation is required in case of isolated increase in troponin in order to consider the possible confounding factors before considering the abnormality as related to the test drug
Troponin I or T elevation > ULN associated with clinical signs or LVEF decrease or ECG abnormality	A cardiac MRI should be performed at the time of the event (as far as possible within 48h to 72h) and 5 to 6 weeks later, for functional cardiac assessment A 24-h Holter should be performed at the time of the event
Troponin I or T elevation > 10 x ULN or troponin increase consistent with the diagnosis of a myocardial infarction (Grade 3)	Discontinue the patient from test drug treatments A cardiac MRI should be performed at the time of the event (as far as possible within 48h to 72h) and 5 or 6 weeks later, for functional cardiac assessment A 24-hour Holter should be performed at the time of the event
Eye Disorders (Results and images of ophthalmic examinations should be made available upon request)	
Other ocular/visual toxicity	
Grade 1 or 2	Maintain dose level and increase ophthalmic monitoring frequency to at least every 14 days Refer the patient to an ophthalmologist within one week for evaluation

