3.4.1. Dose limiting toxicity

Number and percentage of patients with at least one DLT before the end of the first cycle, type of DLT and listing of PTs, verbatim and worst grade of AE declared as DLT will be provided in the DLTES.

Listing of patients with at least one DLT, type of DLT and PTs, verbatim will also be provided in the DLTES.

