Cardiac disorders	
QTcF interval \geq 501 ms or increase of $>$ 60 ms from baseline on at least two separate ECG assessments (1 assessment = triplicate ECG)
 
Asymptomatic, absolute decrease in LVEF of 10% or greater from baseline AND LVEF $<$ 50%
 
Asymptomatic, absolute decrease in LVEF of 20% or greater from baseline
 
Troponin increase $>$ 10xULN or a troponin increase consistent with the diagnosis of a myocardial infarction (Grade 3)
 
Symptomatic congestive heart failure

Skin and subcutaneous tissue disorders	Grade \geq 3 rash
Haematological abnormalities	Grade 4 neutropenia and/or thrombocytopenia persisting for 28 days after the start of azacitidine dosing in a cycle of therapy in the absence of active AML ($<$ 5% blasts) or active MDS or myelofibrosis
Other AEs	
Any Grade \geq 3 AE
 
Single event or multiple occurrences of the same event that lead to a dosing delay of $>$ 7 days in a cycle may be considered to be DLT by the Investigators and the Sponsor, even if not Grade \geq 3
 
Failure to restart test drug administration at the same dose due to drug-related toxicity
 
Failure to restart test drug administration at the same dose within one cycle (i.e. 28 days) of the first missed dose due to delayed recovery from drug-related toxicity
 
Failure to initiate cycle 1 after completing the LID period or failure to receive LID2 after receiving the LID1, due to drug-related toxicity

NCI CTCAE v5.0 will be used for grading	

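### The SAP's troponin table puts every rise above ULN in one class, so it cannot count patients who passed the protocol's own limit of 10 times ULN

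*SAP*

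**What the plan says.** - **SAP 3.4.4.** Table (3.4.4) 2 puts troponin I and troponin T, in separate rows, among the non-gradable parameters. The worst direction is the high one ("High troponin I", and likewise for T). For such parameters the plan is "Descriptive statistics on quantitative value and value by reference ranges at baseline and worst value on treatment according to baseline", using the classes <LLN, [LLN-ULN] and >ULN.
- **SAP 4.2.3.4.** The worst high value of a non-gradable parameter is the raw result if it exceeds ULN, and 0 otherwise. Units are aligned. No value is divided by its ULN.
- **Protocol 4.1.3.5 and SAP Table (4.2.3.1) 1.** Troponin above 10 times ULN is a DLT criterion, alongside "a troponin increase consistent with the diagnosis of a myocardial infarction (Grade 3").
- **Protocol 8.12.** The S64315 dose table has one row for "Grade 1 troponin I or T elevation" and another, leading to discontinuation, for "Troponin I or T elevation > 10 x ULN or troponin increase consistent with the diagnosis of a myocardial infarction (Grade 3"). Sections 8.2.5.4 and 8.2.5.5 also use 10 times ULN as a trigger for cardiac MRI and Holter.
- **Protocol 8.2.5.3.** On the assay: "Either troponin I or T assessment can be used, but it should be ultra-sensitive, whenever possible". Section 8.2 has samples assayed in each hospital's identified laboratory.
- **Protocol 5.4.2, criterion 29.** Troponin above ULN excludes a patient at entry.
- **SAP 3.4.1.** The DLT count is "Number and percentage of patients with at least one DLT before the end of the first cycle", in the DLTES.

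**The concern.** Safety is the primary objective, and SAP 1.2 names cardiac markers among its endpoints. Cardiotoxicity was the dose-limiting toxicity of S64315 alone (protocol 2.2.2), and troponin is sampled five times around each of LID1, LID2, C1D2 and C1D9. A reader of the report will want to know how many patients at each dose level went above 10 times ULN, since that is where the protocol places its DLT and discontinuation criterion. The planned laboratory table cannot answer, because a trivial rise and a very large one share one cell.

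The SAP handles the other cardiac measures differently. QTcF is classed at >500 ms and at a change of >60 ms (3.4.6). LVEF is classed at 40%, 50% and a 10% fall, and is also graded (3.4.7). Troponin has no class near its own limit.

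**Working it through.** No sample size or power figure is involved. The check is whether the limit can be recovered from what the SAP plans to output.

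**Step 1: the classes.** Apply the SAP rule (above ULN if value/ULN > 1) to illustrative multiples.

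| Value/ULN | SAP class | Above 10 times ULN? |
|---|---|---|
| 0.8 | [LLN-ULN] | no |
| 1.1 | >ULN | no |
| 5 | >ULN | no |
| 9.9 | >ULN | no |
| 10.1 | >ULN | yes |
| 50 | >ULN | yes |

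With criterion 29 in force, the baseline-to-worst display is in essence within range against above ULN. Everything from 1.1 to 50 times ULN sits in one cell.

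**Step 2: the raw values.** The ULNs here are assumptions, in arbitrary units; the documents give none. A raw worst value of 120 is
- 120/10 = 12.0 times ULN,
- 120/20 = 6.0 times ULN,
- 120/40 = 3.0 times ULN.

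Only the first is above 10 times ULN. The same number therefore lies on either side of the limit depending on the laboratory.

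**Step 3: the SAP coding on five records.** Take value/ULN pairs 8/10, 9/10, 120/10, 120/40 and 30/40.
- SAP worst-high coding: 0, 0, 120, 120, 0. This shows two records above ULN with the same value.
- Ratios: 0.8, 0.9, 12.0, 3.0, 0.75. This shows one record above 10 times ULN.

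**Step 4: the other outputs.**
- *DLT count (SAP 3.4.1).* It covers the DLTES to the end of cycle 1. SAP 4.2.3.1 takes DLTs as the investigator declared them, without recalculation, and requires at least possible relatedness. A value above 10 times ULN judged unrelated is not a DLT. If that patient then stops before C1D28, SAP 2.1 removes the patient from the DLTES as well.
- *DLT listing (SAP 3.4.1).* It states no cycle limit, so later cases may appear. It still lists declared DLTs only, and a troponin DLT can arise from an infarction-type rise below 10 times ULN.
- *Adverse event tables (SAP 3.4.2).* Worst grade and action taken depend on what was reported as an event. In protocol 8.12, Grade 3 also covers a rise consistent with infarction, so a grade count is not a count of values above 10 times ULN.
- *Withdrawals by period (SAP 3.2.1).* Reasons are given, but not the laboratory value.

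None of these counts the patients who crossed the limit.

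**The case against.** The strongest reply is that such patients are not hidden. Above 10 times ULN the protocol calls for discontinuation, so they should surface in adverse events by action taken, in withdrawals by cycle, or in the DLT listing. Protocol 10.6.2 also plans PK/PD work on troponin, which the SAP leaves to separate plans. The table shells are a separate document (SAP section 1) and might hold a display in multiples of ULN. The dose-limiting cardiotoxicity of monotherapy was reported at 500 mg, whereas doses here go no higher than 250 mg. The report is abbreviated and escalation has stopped.

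Much of this stands as a limit on the point. Individual cases may well be visible, and the shells cannot be judged unseen. It does not supply the count: each of those outputs depends on reporting or attribution, and the SAP text defines no ULN-scaled value for troponin. The abbreviated report drops efficacy but keeps the safety profile.

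Two stronger readings should be resisted.
- A reader might infer that the raw summaries pool troponin I with troponin T. They do not: the rows are separate, and protocol 8.2.5.3 asks for the same subtype throughout. The mixing is of laboratories and assays within each subtype.
- A reader might infer that cases after cycle 1 appear in no DLT output. Only the count table is limited to cycle 1. The lack of a count table for later DLTs, which protocol 10.4.4.2 foresaw, affects every toxicity and is a separate matter.

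**Conclusion.** The point holds for the troponin displays defined in SAP 3.4.4. One class runs from just above ULN to any height, and the raw values cannot be turned back into multiples of ULN from the summary tables. The number of patients above 10 times ULN by dose level, on a primary safety endpoint, is therefore not among the outputs the SAP text defines.

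This rests on three things: eligible patients start at or below ULN, local ULNs differ between laboratories (assumed, since the documents give no values), and the unseen shells do not already add the cut. How many patients are affected is unknown. The documents do not show that any dose decision was altered by this, since escalation used declared DLTs and not this table.

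One related inconsistency should be reconciled: protocol 8.12 speaks of Grade 1 and Grade 3 troponin, while the SAP calls the parameter non-gradable. Nothing here questions the clinical threshold.

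**What to change.** In SAP 3.4.4, with the derivation in 4.2.3.4:

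1. Derive each troponin value as a multiple of the ULN that applied to that sample (its own laboratory and subtype).
2. For each patient in the Safety Set, take the worst on-treatment ratio over the treatment period including the LID. Present counts for up to ULN, above ULN to 10 times ULN, and above 10 times ULN, by dose level and overall, keeping troponin I and T identified.
3. Add a patient listing of value/ULN with subtype and cycle, so that timing is visible without splitting a small table further.

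The cut at 10 comes from the protocol. No intermediate cut, such as 3 times ULN, is needed, and the documents offer no source for one.

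Cost: one derived variable, one small table and one listing. Reference ranges are collected (protocol 8.2) and held in the database (SAP 4.2.3.4), so no new data are required. This is a free improvement.
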